4.1 Selection of Study Population

Approximately 60 patients will be enrolled at approximately 30 sites in the United States, Europe, and Australia. Patients will be assigned to study treatment only if they meet all of the inclusion criteria and none of the exclusion criteria.

Deviations from the inclusion and exclusion criteria are not allowed because they can potentially jeopardise the scientific integrity of the study, regulatory acceptability, or patient safety. Therefore, adherence to the criteria as specified in the protocol is essential. Rescreening of patients that failed the initial screening may be done if the patient fulfils selection criteria upon a subsequent visit. However, this may only be done for some of the criteria, as specified below.

4.1.1 Inclusion Criteria

Each patient must meet all of the following criteria to be enrolled in this study:

1. Is at least 18 years old at the screening visit (Visit 1). – Re-screening possible if initial screening was soon before 18th birthday.
2. Has a diagnosis of FECD at Visit 1. – Rescreening is not possible.
3. Has confluent central guttae in the study eye that can be removed by descemetorhexis of a circular area of [REDACTED] diameter or less (at Visit 1). – Rescreening is not possible.
4. Has a study eye with best corrected visual acuity (BCVA) of 75 letters or fewer by Early Treatment Diabetic Retinopathy Study (ETDRS) testing (Snellen equivalent of 20/32 or worse) at Visit 1. – Rescreening is not possible.
5. The study eye descemetorhexis at Visit 2 is confirmed to have excised a central area with confluent guttae and a diameter of [REDACTED]. Guidance for performing the study eye descemetorhexis and measurement of the excised area will be provided in the study manual. – Rescreening is not possible in that eye but the non-study eye can be used.

6. Can understand the written informed consent, provides signed and witnessed written informed consent, and agrees to comply with protocol requirements before any study-specific assessment is performed. – Rescreening is not possible.

4.1.2 Exclusion Criteria

Patients meeting any of the following criteria will be excluded from the study:

1. Is a female patient and any of the following is true:
 - is pregnant or lactating/breastfeeding, or
 - is not surgically sterile, not post-menopausal (no menses for the previous 12 months), or not practising an effective method of birth control as determined by the investigator (eg, oral contraceptives, double barrier methods, hormonal injectable or implanted contraceptives, tubal ligation, or partner with vasectomy).

If a patient is female and of childbearing potential, she must have a negative urine pregnancy test result at Visit 2 before the descemetorhexis. Women of childbearing potential must also agree to use effective contraception throughout the study.

A female of childbearing potential is defined as a woman who has experienced menarche and has not undergone successful surgical sterilisation or is not post-menopausal, and a post-menopausal woman is defined as having had no menses for the previous 12 months (without a known cause).

– Rescreening is possible if patient either stops nursing or initiates birth control.

2. Has a study eye with confluent guttae in the periphery or confluent guttae outside the stripped area (individual guttae are allowed).

Note that patients may have individual or small number of guttae remaining outside the stripped area, but there should be no areas of confluent guttae remaining after the descemetorhexis. For example, a patient who had 5 to 10 guttae remaining in a few spots around the circumference of the descemetorhexis would not be excluded by this criterion. – Rescreening is not possible.
3. Has a study eye with a history of cataract surgery within 90 days of Visit 1.

– Rescreening is possible.

4. Has a study eye with a history of any previous ocular surgery other than for cataract. – Rescreening is not possible.
5. Has a non-study eye with a history of any previous ocular surgery within 30 days of Visit 1. – Rescreening is possible.
6. Plans to receive any surgical treatment on the study eye during any study period, other than the study descemetorhexis. – Re-screening possible if during initial screening subject had plans for surgical treatment on the study eye during the study period, but upon re-screening these plans for surgery were cancelled.
7. Plans to receive any surgical treatment for FECD or cataract on the non-study eye in the screening or treatment period. – Re-screening possible if during initial screening subject had plans for surgical treatment for FECD or cataract on the non-study eye during the screening or treatment period, but upon re-screening these plans for surgery were cancelled.
8. Has advanced corneal stromal oedema defined as the presence of widespread haze or bullae on slit-lamp examination. – Rescreening is not possible.
9. Has a study eye with central corneal thickness $\geq 670 \mu\text{m}$. – Rescreening is not possible.
10. Has known severe comorbidities that may interfere with descemetorhexis (e.g., a bacterial, viral, or fungal ophthalmic infection). – Rescreening is not possible.
11. Has any clinically significant ocular condition other than FECD or cataract that requires medication or ocular surgery (described in Section 5.8.3). – Rescreening is not possible.
12. Has diabetes with poor blood sugar control (eg, HbA1c value $> 8.5\%$). – Re-screening possible if HbA1c has improved at the time of the re-screening.
13. Has used contact lenses within 7 days of Visit 1. – Rescreening is possible.
14. Has hypersensitivity to any ophthalmic medication used for diagnosis or treatment, including eye drops containing antibiotic(s) or glucocorticoid(s). – Rescreening is not possible.
15. Has known hypersensitivity to any component of the study drugs. – Rescreening is not possible.

16. Has previously used ripasudil, netarsudil, or other ROCK inhibitors. – Rescreening is not possible.
17. Has used any investigational medications within 30 days of Visit 1. – Rescreening is possible.
18. Has a positive urine test result for drugs of abuse (opiates, methadone, cocaine, amphetamines, barbiturates, or benzodiazepines) or alcohol at screening. – Rescreening is not possible.
19. Has donated more than 450 mL of blood within 60 days of Visit 1. – Rescreening is possible.
20. Is a member or a family member of the professional or ancillary personnel working at the study site or the sponsor involved in the study. – Rescreening is not possible.
21. Has a concomitant medical or psychological condition that could interfere with study participation or is otherwise not suitable for entry into the study in the opinion of the investigator. – Re-screening possible if investigator provides evidence that the concomitant medical or psychological condition resolved and the subject was suitable for entry into the study.

4.2 Discontinuation of Treatment and Withdrawal of Patients From the Study

The duration of the study is defined for each patient as the date signed written informed consent is provided through the date of the last study visit attended.

There are 3 scenarios that result in interruption of the treatment regimen. Interruption of treatment is defined as a temporary stopping of study drug treatment that resumes during the treatment period, due to an AE or any other reason. Early discontinuation of treatment is defined as permanent stopping of study drug treatment before completing Visit 9, scheduled for Week 12. Investigators will strive to ensure that a patient who has interrupted treatment for a particular reason will not discontinue treatment unless discontinuation is medically imperative in the investigator's judgement. Early withdrawal from the study is defined as failing to complete Visit 14, scheduled for Week 52.

Study drug administration may be discontinued early at the discretion of the investigator (or designee) if the patient does not tolerate the dosing regimen or if, in the investigator's judgement, the patient's health may be jeopardised by continuing study treatment. Patients who discontinue treatment during the study will be encouraged by investigators to continue to participate in all scheduled study site visits and assessments, and study data will be collected for these patients per protocol. Every effort must be made to keep patients in the study (see Section 5.8.2 for a discussion of treatment discontinuation after rescue surgical procedures).

4.2.1 Reasons for Discontinuation or Withdrawal

Patients may discontinue treatment or withdraw from the study at any time and for any reason without prejudice to their future medical care by the investigator or at the study site. Every effort must be made to keep patients in the study. The reasons for patients discontinuing treatment or withdrawing early will be recorded.

A patient may discontinue treatment or be discontinued from treatment for any of the following reasons:

1. The patient does not meet the protocol inclusion or exclusion criteria.
2. The patient is non-compliant with the protocol.
3. The patient has a serious or intolerable AE that, in the investigator's opinion, requires withdrawal from the study.
4. The patient has symptoms or an intercurrent illness not consistent with the protocol requirements or that justify withdrawal.
5. The patient undergoes rescue keratoplasty (Section 5.8.2).
6. Other reasons (eg, pregnancy, development of contraindications of use of study drug).

A patient may be withdrawn from the study for any of the following reasons:

1. The patient withdraws consent.
2. The patient is lost to follow-up.

The investigator will also withdraw all patients if Kowa Research Institute, Inc. terminates the study. The study may be terminated if it becomes apparent that the objectives of the trial cannot be met, or if the frequency or pattern of AEs reported in the trial indicate that the drug is no longer likely to have a positive benefit-to-risk ratio.

4.2.2 Handling of Withdrawals

Patients who withdraw from the study or who are withdrawn from the study will no longer receive study drug. When a patient withdraws or is withdrawn from the study, the reason(s) for withdrawal shall be recorded by the investigator on the relevant page of the electronic case report form (eCRF).

Whenever possible, all patients who withdraw from the study early will undergo all EOS assessments. Patients who fail to return for final assessments will be contacted by the site with 2 documented telephone calls followed by 1 registered letter, as needed, to have them comply with the protocol.

It is vital to obtain follow-up data on any patient withdrawn because of an AE or serious AE (SAE). In every case, efforts must be made to undertake protocol-specified safety follow-up procedures.

4.2.3 Replacements

Patients who are screened for the study and receive a study descemetorhexis may be replaced if they never are randomly assigned study drug or are withdrawn from the study before they administer any study drug. The replacement patients will receive a new randomly assigned treatment and not the treatment assignment of the replaced patient. Patients who self-administer any study drug and subsequently are withdrawn early from the study will not be replaced. Patients who fail to satisfy inclusion and exclusion criteria at screening may be rescreened 1 additional time at the discretion of the sponsor. A special case and conditions for replacement, in case the descemetorhexis fails on the first-selected study eye, is presented in Section [5.8.3.1](#).

5 Study Drug Treatments

5.1 Method of Assigning Patients to Treatment Groups

After confirmation that the study eye descemeterhexis satisfied inclusion criterion 5 (Section 4.1.1) and any pregnancy test is negative (exclusion criterion 1, Section 4.1.2), patients will be randomly assigned at Visit 2 to either placebo, K-321 BID, or K-321 QID treatment (Section 5.2) using a 1:1:1 allocation ratio. An interactive web response system (IWRS) will be used to administer the randomisation schedule. An independent [REDACTED] biostatistician will generate the randomisation schedules using SAS software Version 9.4 (SAS Institute Inc, Cary, North Carolina) or later. The IWRS will link sequential patient randomisation numbers to treatment codes. The randomisation schedule will use an appropriate block size, which will not be revealed other than to the [REDACTED] and Kowa biostatisticians.

5.2 Treatments Administered

There are 3 treatment groups: K-321 ophthalmic solution 0.4% dosed QID (K-321 QID), K-321 ophthalmic solution 0.4% dosed BID (K-321 BID); and placebo. To preserve masking, all patients will self-administer assigned study drug QID and will dose from [REDACTED], one to be used M/N and the other to be used MD/E, as presented in Table 5-1.

Table 5-1 Vial Contents by Dosing Regimen and Dosing Time for Each Treatment Group From Day 1 to Visit 9 (Week 12)

Treatment	Morning	Mid-day	Evening	Night
K-321 QID	K-321 0.4%	K-321 0.4%	K-321 0.4%	K-321 0.4%
K-321 BID	K-321 0.4%	Placebo	Placebo	K-321 0.4%
Placebo	Placebo	Placebo	Placebo	Placebo

Except on days of study visits on Day 1 through Week 12 (not including Visit 9) during the treatment period, study drug will be dosed by the patient QID: morning (9 AM \pm 1 hour), mid-day (1 PM \pm 1 hour), evening (5 PM \pm 1 hour), and night (9 PM \pm 1 hour). Each patient will be provided with 2 sets of colour-coded [REDACTED], one set to be applied M/N and the other to be applied MD/E. See Section 5.4.1 for a detailed description of packaging.

On study visit days Visit 3 through Visit 9, patients will not apply any study drug until after all study measurements have been completed; thereafter on those days, patients will start dosing with the dose closest in timing to the dosing regimen and continue with the remaining doses for the day. Additionally, on Visit 3 they must first apply study drug within [REDACTED] after the end of the descemetorhexis procedure on Day -1 (Visit 2).

With the primary efficacy endpoint being assessed at Visit 9 (Week 12), if a patient applies any study drug on the day of Visit 9 before all study measurements have been completed, that patient's Visit 9 should be rescheduled within the visit window allowance (eg, the next day). For visits other than Visit 9 during the treatment period, a patient who applies study drug before all study measurements have been completed will be assessed as planned, and a protocol deviation must be recorded.

At Visit 9 (Week 12), patients will enter the drug-tapering phase of the follow-up period, and new study drug will be dispensed without M/N or MD/E colour coding (Section 5.2). All patients will self-administer their tapering-phase study drug BID (9 AM \pm 1 hour and 9 PM \pm 1 hour) for a week, then once daily (9 AM \pm 1 hour) for a week, and then will discontinue study drug. At Visit 9, patients will apply the first dose of study drug [REDACTED] of completing study measurements and will apply the second dose at night, as scheduled. However, if the first dose will be applied after 8 PM, the second dose must be skipped.

For each dose, patients must instil 1 drop to the study eye only and then close the eyelids, pressing on the lacrimal punctum. Patients will be advised to keep the eye closed for 1 to 5 minutes before opening the eye. Any other concurrent ocular medication(s) must be applied at least 5 minutes following instillation of study drug. Patients will be trained by site staff on the application of eye drops.

5.3 Identity of Study Drug

The K-321 ophthalmic solution contains ripasudil 0.4% (4.896 mg/mL of ripasudil hydrochloride hydrate, equivalent to 4.0 mg/mL as the free base) in a solution also containing the excipients sodium dihydrogen phosphate and sodium hydroxide at a pH in the range of 5.0 to 7.0. The solution is isosmotic to normal saline, clear, colourless, and [REDACTED]. The placebo ophthalmic solution is identical in appearance, osmolarity, and pH to the K-321

ophthalmic solution except it does not include ripasudil. [REDACTED]

The following drug supplies will be used in the study:

Product	Supplied As	Strength
K-321	ophthalmic solution	0.4%
Placebo (vehicle)	ophthalmic solution	0%

[REDACTED] will manufacture study drug.

5.4 Management of Clinical Supplies

The sponsor will supply sufficient study drug to study sites.

5.4.1 Study Drug Packaging and Storage

Study drug will be prepared in boxed kits [REDACTED] and shipped by Catalent UK Packaging Ltd. Each pack will contain randomly assigned dosing for 1 patient and will contain a more than sufficient quantity for dispensing during the double-masked treatment period (Table 6-1).

Study drug must be stored in a secure area (eg, a locked cabinet), protected from moisture, and kept at controlled room temperature [REDACTED].

[REDACTED] will be filling [REDACTED] with study drug. The [REDACTED] will [REDACTED] [REDACTED] for clinical use at Catalent UK Packaging Ltd. (Westhoughton, Bolton, Lancashire, UK). Study drug is packaged [REDACTED] [REDACTED] being M/N doses, MD/E doses, or tapering-phase doses). The different [REDACTED] and [REDACTED] will have different coloured labels. [REDACTED]

[REDACTED]. Kit labels provide the following information: protocol number., kit number., lot number, patient identification number, study site, investigator, dosing directions, storage requirements, cautionary statements, and country-specific clinical labelling content requirements. Study drug will be dispensed to

selected clinical supply depots where shipments to clinical sites are managed via the IWRS system.

The materials schedule will be prepared by an independent [REDACTED] biostatistician and provided to the IWRS and the packaging vendor. At the time of randomisation, the IWRS will assign each patient a study drug kit corresponding to the patient's randomly assigned treatment based on the drug supply inventory that is available at the site. The kit will be identified by a unique kit number that is separate from the patient or randomisation numbers. The IWRS will administer study drug dispensing at each visit indicated in [Table 6-1](#).

5.4.2 Study Drug Accountability

The investigator will maintain accurate records of receipt of all study drug, including dates of receipt. In addition, accurate records will be kept regarding when and how much study drug is dispensed and used by each patient in the study. Reasons for departure from the expected dispensing regimen must also be recorded. At the completion of the study, to satisfy regulatory requirements regarding drug accountability, all study drug will be reconciled, shipped from study sites to Catalent depots in the United States and Germany, and destroyed according to applicable regulations.

5.5 Medication Errors

At Visit 3, patients will be given instructions on how to administer their assigned ophthalmic solution and how to avoid contaminating the [REDACTED] solution, and they will be observed instilling their own drops by the site staff. Re-education on the proper administration procedure will be given to patients by study site staff throughout the treatment period at each visit. To minimise medication errors during the 12-week treatment phase, [REDACTED] and [REDACTED] will be colour-coded differently for M/N and MD/E doses.

5.5.1 Treatment of Medication Errors

In the event of a medication error, the appropriate supportive clinical care must be provided as dictated by the patient's clinical status.

5.5.2 Overdose Management

A symptomatic overdose from topical administration is unlikely, as no overdose was observed during the development of Glanatec (Kowa Company Ltd 2019). Patients will be instructed to contact the investigator or study coordinator immediately in the event of a suspected symptomatic overdose. Suspected symptomatic overdoses must be reported as AEs (or SAEs) in the eCRF. In the event of overdose, the appropriate supportive clinical care must be provided as dictated by the patient's clinical status

5.5.3 Missed Doses

If a dose is missed, patients will be advised as follows:

- If you notice you missed a dose 2 hours or less after a scheduled dose time, dose immediately
- If you notice you missed a dose more than 2 hours after a scheduled dose time, skip the dose you missed and resume regular dosing at the next planned time according to the schedule. A missed night dose may be taken at any time until midnight of the same day.

5.6 Masking

Study drug will be double-masked. All study drug will be supplied in identical packaging, colour, smell, and appearance to enable double-masked conditions. K-321 and matching placebo will be provided in identical packaging so that all investigators, study site staff, patients, and clinical monitors will remain masked throughout the study. The IWRS will assign study drug to patients at the time of randomisation. Only personnel in IWRS, the independent randomisation team within [REDACTED] Biostatistics, and clinical supplies will be unmasked and will have access to treatment assignments; all other parties involved in the study will be fully masked.

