5.6.1 Unmasking Treatment

A patient's treatment assignment will not be unmasked for the investigator or study site staff until the EOS unless medical treatment of the patient depends on knowing the study treatment the patient received. In the rare event that unmasking is needed because of a

medical emergency, the investigator may unmask an individual patient through the IWRS. Reasons for treatment unmasking must be clearly explained and justified in the eCRF. The date on which the code was broken together with the identity of the person responsible must also be documented.

Patients who are unmasked will be allowed to continue their participation in the study; however, their data may be excluded from per-protocol analyses.

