7.7.1 Analysis of Primary Efficacy Endpoint

The primary analysis of central corneal ECD will be performed on the study eye within the FAS via a Wilcoxon rank sum test and will be based on assessments performed by specular microscopy. Testing will be performed in a pairwise manner with each dosing regimen (QID and BID) of K-321 0.4% compared to placebo. For each dosing regimen, the following 2-sided hypothesis will be tested

$H_0: \Delta = 0$ versus $H_a: \Delta \neq 0$

where Δ is the shift in location in central corneal ECDs between the active and placebo groups being compared: ie,

$X_i = e_i$ for $i = 1$ to n for the placebo patients

$Y_j = e_j + \Delta$ for $j = 1$ to m for the K-321 patients

The Hodges-Lehmann estimate (Hodges and Lehmann 1963) for the shift in location (eg, the median of all differences $d=Y_j - X_i$) and Moses 95% CI (Moses 1965) will also be presented.

Week 12 assessments that are unable to be performed due to corneal oedema will be [REDACTED]
[REDACTED]
[REDACTED].

Week 12 assessments that are [REDACTED] due to patient withdrawal or missed visit will be [REDACTED]. Patients who receive a rescue keratoplasty performed prior to Week 12 will be [REDACTED]
[REDACTED]
[REDACTED]
[REDACTED]
[REDACTED]

Sensitivity analyses will be performed by repeating the above analysis and [REDACTED] [REDACTED] for the PPS. The primary analysis methods will also be repeated for the FAS using [REDACTED]
[REDACTED] Additionally, analyses will be performed using assessments performed by HRT for the subset of patients for which the assessments are available.

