7.7.6 Interim Analyses

No interim analyses will be performed. The primary analysis will be conducted at the Week 12 database lock ie, after all patients have completed dose tapering at the Week 16 visit or have been discontinued from the study and/or treatment before this visit. Analysis of the complete study data (through Week 52) will be performed after all patients have completed the Week 52 visits or have been discontinued from the study before the Week 52 visit. As the primary efficacy endpoint is at the Week 12 visit, no alpha adjustments will be required. No changes to study conduct (eg, change to sample size or early stopping) are planned.

8 Data Quality Assurance

The sites will maintain source documentation and enter patient data into the eCRF as accurately as possible and will rapidly respond to any reported discrepancies. Electronic CRFs are accessed through Medidata Rave[®] (Medidata Solutions Inc, New York, New York). This EDC system is validated and compliant with US Title 21 Code of Federal Regulations (CFR) Part 11. Each person involved with the study will have an individual user name and password that allows for record traceability. Thus, the system, and subsequently any investigative reviews, can identify coordinators, investigators, and individuals who have entered or modified records, as well as the time and date of any modifications. A quality review of the data will be performed by the site with additional reviews by the clinical monitor through source data verification.

Each eCRF is presented as an electronic copy, allowing data entry by site staff, who can add and edit data, identify and resolve discrepancies, and view records. This system provides immediate direct data transfer to the database, as well as immediate detection of discrepancies, enabling site coordinators to resolve and manage discrepancies in a timely manner.

Paper copies of the eCRFs and other database reports may be printed by the investigator. This system provides site staff, monitors, and reviewers with access to hard copy audits, discrepancy reviews, and investigator comment information.

After all data reviews and query resolutions are complete, the SAP is approved and signed, and any summary/analysis populations are approved, the database will be locked.

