## 1. Introduction

This statistical analysis plan (SAP) addendum to the primary SAP v2.0, dated August 25, 2021, is to describe additional analyses that were defined **after the Week 12 Unmasking** to support the final CSR. All analyses that were defined in the primary SAP v2.0 prior to the Week 12 unmasking will not be described again in this document.

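### Section 5.6 says everyone outside three groups stays fully masked, but codes are opened at the Week 12 lock while follow-up runs to Week 52

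*Protocol*

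**What the plan says.** Protocol Section 5.6 makes two masking statements. The specific one is that "all investigators, study site staff, patients, and clinical monitors will remain masked throughout the study". The general one lists IWRS personnel, the independent randomisation team and clinical supplies as the only holders of treatment assignments, and adds that "all other parties involved in the study will be fully masked". Neither has an exception for a Week 12 analysis. Section 5.6.1 adds that a patient's assignment "will not be unmasked for the investigator or study site staff until the EOS unless medical treatment of the patient depends on" knowing it.

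Section 7.7.6 sets two analysis points. For the first: "The primary analysis will be conducted at the Week 12 database lock", which it places after every patient has reached Week 16 or discontinued. For the second: "Analysis of the complete study data (through Week 52) will be performed after all patients have completed the Week 52 visits", or have discontinued earlier.

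Section 7.7.1 defines the primary comparison: "Testing will be performed in a pairwise manner with each dosing regimen (QID and BID) of K-321 0.4% compared to placebo".

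The supplied SAP is an addendum to a primary SAP v2.0 that is not among the documents. Its introduction says the new analyses were defined after the Week 12 unmasking, for the final study report, and that analyses set out in v2.0 "prior to the Week 12 unmasking will not be described again".

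**The concern.** The protocol claims a masking property that its own analysis schedule does not allow. A pairwise test against placebo cannot be run without treatment codes, so someone works with unmasked data from the Week 12 lock onward, while Week 20 to Week 52 data are still to be collected and cleaned for some patients.

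The stake is the long-term part of the trial. Section 2.2 sets secondary objectives for ECD, thickness, clarity and safety out to 52 weeks. Some of the later data involve judgement: oedema is graded present or absent (Section 6.2.3), rescue keratoplasty depends on the investigator's view of healing (Section 5.8.2), ECD is read from images sent out for analysis (Section 6.2.1.1), and slit-lamp photographs go to the sponsor (Section 6.3.1). The addendum's rescue-therapy endpoint also counts as events certain patients who left the study and might have gone on to surgery or to a Rho kinase inhibitor (notes to Table 14.2.1.42). Assigning a withdrawal to that category is a judgement, in an endpoint defined after unmasking. If those who make such judgements know the by-arm results, or the arm, bias is possible. A report that calls the whole trial fully masked would also be inaccurate.

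**Working it through.** There is no planned figure to reproduce. The check compares the texts and then counts the exposed follow-up.

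**Can the statements all be true?**

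1. Section 5.6 gives a closed list of three unmasked groups, with no end date.
2. Sections 7.7.1 and 7.7.6 require a between-arm analysis at the Week 12 lock, which needs the codes.
3. The addendum's introduction confirms that an unmasking took place at that stage and that further analyses were defined after it.
4. Either people outside the three groups received codes or by-arm results, or one of the three groups also ran the analysis and kept its results. The text provides for neither. Section 7.7.6 covers alpha and study conduct, but not who receives codes or results.

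**Who is covered by which statement?**

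- Investigators, site staff, patients and monitors: covered by the specific sentence in Section 5.6, and the first two also by Section 5.6.1. Nothing in Section 7.7.6 or the addendum contradicts this.
- Image readers, data managers and sponsor reviewers: covered only by the general sentence, the one that fails after the lock.
- By-arm results, as distinct from individual assignments: not mentioned for anyone in Sections 5.6 or 5.6.1. There is no safety monitoring committee (Section 6.4) and no external data monitoring committee (Section 11.1.1), so no independent body is named to hold them.

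**How much follow-up is exposed?**

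Inputs from Table 6-1: the Week 16 window is days 105-119 and the Week 52 window is days 357-371. Visits after Week 16 fall at Weeks 20, 24, 38 and 52.

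- Last patient, nominal: 52 − 16 = 36 weeks.
- Last patient, by windows: 357 − 119 = 238 days (34 weeks) to 371 − 105 = 266 days (38 weeks).
- Visits remaining: 4 of the 5 in follow-up.

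For any other patient, let *a* be the weeks by which that patient reached Week 16 ahead of the last patient, and *L* the weeks from the last patient's Week 16 visit to the opening of the codes. Exposed follow-up is max(0, 36 − *a* − *L*) weeks. The later visits fall 20 − 16 = 4, 24 − 16 = 8, 38 − 16 = 22 and 52 − 16 = 36 weeks after Week 16, so the visits still to come are:

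- *a* + *L* under 4 weeks: 4
- 4 to under 8: 3
- 8 to under 22: 2
- 22 to under 36: 1
- 36 or more: 0

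Neither *a* nor *L* is given. Section 8 requires data review and query resolution before a lock, so *L* is above zero and 36 weeks is a nominal ceiling.

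**The case against.** The strongest reply is that this is a wording gap with little bias behind it. The people who generate the judgement-based data are those the specific sentence keeps masked: the investigator grades oedema, decides on rescue and records withdrawal reasons (Section 4.2.2), and the monitor documents deviations (Section 11.2.2). No text places an unmasked person in any of these steps. Thickness is an instrument reading, and no listed endpoint comes from the sponsor's review of slit-lamp photographs. The staged analysis is openly planned, with no change to study conduct intended. SAP v2.0 may contain an unmasking plan. And because the unmasking has already happened, new wording cannot restrict past access.

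Most of this stands, and it rules out several stronger readings that a reader might infer:

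- That Section 5.6 leaves these staff with unrestricted access. It does not: it bars codes to everyone outside three groups. The fault is that the bar cannot hold as written after the lock.
- That sites, patients or monitors were unmasked. Nothing shows this.
- That the sponsor's analysts were the ones unmasked. The documents do not say who was.
- That the Week 52 secondary results rest on per-protocol classification. Section 7.7.2 uses the FAS; only selected analyses are repeated in the PPS, and Section 8 has analysis populations approved before lock.

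The reply leaves three things unanswered. A plan in SAP v2.0 would not correct the unqualified sentence in Section 5.6. Masking sites to codes does not keep group results from them. And the text does not say who classifies withdrawals for the rescue endpoint. The addendum discloses when that endpoint was defined, but not whether those who classify its events are masked.

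**Conclusion.** The blanket masking statement is wrong for the period after the Week 12 lock. The conclusion rests on the need for codes in the primary analysis and on the addendum's explicit reference to an unmasking. For the last patient the period is nominally at most 36 weeks (34 to 38 by the visit windows) and four visits; it is shorter for earlier patients and shorter still if the codes were opened some time after the last Week 16 visit.

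A reader might infer that the primary result is compromised. It is not: the Week 12 data are collected and locked before the codes are opened. Nor do the documents show bias in the later data. What remains is a risk that by-arm results reach sites, image readers or those who query or classify post-lock data, most plainly in the withdrawal-based rescue events. SAP v2.0 was not available and could narrow this risk if it contains access rules.

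**What to change.** - Amend Sections 5.6 and 7.7.6 to name the roles unmasked at the Week 12 lock.
- State that neither treatment codes nor by-arm results go to sites, patients, monitors, image readers or anyone who queries or classifies post-lock data until the final lock. For sites, patients and monitors, the new element is the by-arm results.
- Have withdrawal reasons for the rescue endpoint classified by staff masked to arm and to by-arm results.
- In the study report, state who was unmasked and when, without assuming it was the sponsor's analysts, and do not describe Weeks 16 to 52 as fully masked.

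If follow-up has already ended, the access rule can no longer act. The remedy is then a record of who had codes or results and from what date, with masked classification of any withdrawals still to be adjudicated.

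The cost is protocol and SAP wording, access control on the Week 12 outputs, and narrower circulation of those results until the final lock. No patients or visits are added.
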